4.2.5 Subgroups

Analyses will be performed on the following subgroups:

- Investigator center (France, US)
- Known cardiac abnormality (with, without)
- Body mass index (< 25, [25, 30[, ≥ +30)
- Exam sequence number ([1-10], [11-20], [21-30])

4.3 Handling of Missing Data

Missing data will not be replaced in the statistical analysis. The number of missing data will be specified in the analysis.

5. Analysis Plan

5.1 Patient Enrollment and Disposition

Participant enrollment and follow-up are described based on the study profile as defined in the CONSORT recommendations. A summary table and a flowchart will present for each population the number of participants at each assessment.

The following analysis will be performed:

- Number of patients in the screened population (total, and for each site).
- Number of patients in the eligible population (total, and for each site) and reasons for non-eligibility will be described for patients excluded from the eligible population.
- Number of patients in the FAS population (total, and for each site) and reasons for non-eligibility will be described for patients excluded from the FAS population.
- Number of patients in the SAF population (total, and for each site).
- Number of patients (total, and for each site) who have the exam performed by:
 - a novice and the 5 reviews,
 - an expert and the 5 reviews,
 - both novice and expert and the 5 reviews.

The number and percentage of patients who withdrew from the study and the reasons for withdrawal will be presented overall and by site. The time between inclusion and withdrawal (in days) will also be presented.

5.2 Demographics and Anthropometric Characteristics

All demographics and anthropometric characteristics will be performed on the FAS population and according to the site. A comparison of demographics and anthropometric characteristics between sites will be performed.

Quantitative analyses will be performed on the following variables:

- Age (in years),
- Height (in cm),
- Weight (in kg),
- BMI (in kg/m²).

Qualitative analyses will be performed on the following variables:

- Sex with the following categories:
 - Male
 - Female
 - Other
- BMI with the following categories:
 - BMI < 25 kg/m²
 - 25 ≤ BMI < 30 kg/m² (overweight)
 - BMI ≥ 30 kg/m² (obese)
- Ethnicity with the following categories:
 - Hispanic or Latino
 - Not Hispanic or Latino
 - Unknown / Not Reported
- Race with the following categories:
 - White
 - Black / African American
 - Asian
 - American Indian / Alaska Native
 - Unknown / Not Reported
 - Other

5.3 Medical History

On the FAS population, the following qualitative analyses will be performed:

- Indications, classified in the following categories: respiratory pathology, pulmonary hypertension, pericardial effusion, cardiotoxic drugs, endocarditis, hypertrophic cardiomyopathy, rhythm disorders, valvulopathy, dilated cardiomyopathy, cardiovascular risks/symptoms, valve prosthesis/valvuloplasty, ischemic heart disease, heart transplant follow up, other, not reported,
- Prior cardiac diagnoses,
- Prior non-cardiac diagnoses,
- Implemented medical devices,
- Cardiac abnormalities.

Other prior cardiac diagnoses, other prior non-cardiac diagnoses, other implemented medical devices, and other cardiac abnormalities will be described in listings (and translated into English when required).

See section 2.1 to see the categories for each variable.

5.4 Primary and Secondary Endpoints Analyses

5.4.1 Primary Endpoints Analysis

The analyses will be performed on the FAS population.

For the 4 primary endpoints, the number and percentage of achievement of qualitative visual assessment according to cardiologist review (at least 3 of 5 cardiologists answer “yes”, that is to say, the majority) and its 95% CI will be evaluated for the novice and the expert. The 95% CI will be computed *via* an MRMC analysis.

For comparison, the difference between the percentage of success for the novices’ exams and the percentage of success for the experts’ exams will be computed, in patients from the FAS population who have exams performed by both novices and experts.

In secondary analyses of primary endpoints, the same analysis will be performed on each subgroup (investigator center, known cardiac abnormality, body mass index, and exam sequence number), depending on the number of patients in each subgroup.

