ANALYSIS	
Patient description: The population will be described in terms of demographics, ultrasound parameters, and pathology.
 
Endpoints: For all quality criteria, the percentage of success and its confidence interval will be evaluated for acquisitions performed by experts and acquisitions performed by novices. This analysis will be performed via a multi-reader, multi-case power analysis.
 
For each qualitative ultrasound measurement, taking into account the experts' acquisition as the reference, the following parameters will be evaluated:
 
 
● Percentage of agreement
 
● Sensitivity
 
● Specificity
 
● Precision
 
● Recall
 
● F1-score
 
● Area under the curve
 
 
For each quantitative ultrasound measurement:
 
 
● The mean, standard deviation and 95% confidence interval of the difference will be calculated between the measurements made on the acquisitions obtained by the experts and those obtained by the novices
 
● Bland-Altman plots and correlation plots will be performed.
 
 
Sensitivity studies will be performed on the investigating centers, prior cardiac diagnoses, and obese patients.

DESKi	PROSPECTIVE EVALUATION OF HEARTFOCUS: A SOFTWARE SUPPORTING THE ACQUISITION OF CARDIAC ULTRASOUND EXAMS	HF-01 Version:4.2
-------	---------------------------------------------------------------------------------------------------------	----------------------

	The evaluation of HeartEF will be performed by comparing the results from the algorithm to the manual cardiologist's analysis.
--	--------------------------------------------------------------------------------------------------------------------------------

EXPECTED IMPACTS	
From a medical point of view, there will be no direct benefit for the patient included in the analysis.
 
At a larger scale, HeartFocus software will outlook access to ultrasound exams by allowing non-experts (emergency physicians, residents, general practitioners, paramedics, and nurses) to acquire cardiac ultrasound exams of sufficient quality for their analysis, without any previous experience in echography.
 
This would improve patient management by optimizing the care pathway, with echography being used as a screening or follow-up tool for patients.

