3.2 Secondary Objectives

The secondary objectives are:

- to evaluate the agreement between the acquisitions obtained by experts and those obtained by novices in terms of quality and echocardiographic parameters,
- to evaluate the impact of the investigating centers, prior cardiac diagnoses, and obese patients on the quality of ultrasound exams,
- to evaluate the time to acquire a limited ultrasound exam for a novice with the HeartFocus software,
- to evaluate the performance of HeartEF to automatically calculate the ejection fraction.

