5.4.2.1 Quality Endpoints Analysis

For the quality endpoints (enumerated in section 3.4.1), the number and percentage of achievement of qualitative visual assessment according to cardiologist review (at least 3 of 5 cardiologists answer “yes”, that is to say, the majority) and its 95% CI will be evaluated for the novice and the expert. The 95% CI will be computed *via* an MRMC analysis.

For comparison, the difference between the percentage of success for the novices’ exams and the percentage of success for the experts’ exams will be computed, in patients from the FAS population who have exams performed by both novices and experts.

In secondary analyses of quality endpoints, the same analysis will be performed on each subgroup (investigator center, known cardiac abnormality, body mass index, and exam sequence number), depending on the number of patients in each subgroup.

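### The impact of centre, prior cardiac diagnosis and obesity is a stated objective, but no difference between subgroup levels is planned with a confidence interval.

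*SAP*

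**What the plan says.** SAP 3.2 lists as a secondary objective "to evaluate the impact of the investigating centers, prior cardiac diagnoses, and obese patients on the quality of ultrasound exams". The protocol synopsis has the same objective. Its Analysis section adds only that "Sensitivity studies will be performed on the investigating centers, prior cardiac diagnoses, and obese patients", with no method or contrast.

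The SAP carries this out in two places. For the primary endpoints, 5.4.1 states that "the same analysis will be performed on each subgroup", naming centre, known cardiac abnormality, BMI and exam sequence number, subject to the condition "depending on the number of patients in each subgroup", for which no threshold is given. For the quality endpoints, 5.4.2.1 repeats the rule: "In secondary analyses of quality endpoints, the same analysis will be performed on each subgroup".

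The analysis being repeated has two parts:
- the number and percentage of exams judged assessable by a majority of the five cardiologists, for novices and for experts, with a 95% CI from a multi-reader multi-case (MRMC) analysis;
- in patients with both exams, "the difference between the percentage of success for the novices’ exams and the percentage of success for the experts’ exams will be computed". No CI is stated for this difference.

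SAP 4.2.5 defines the subgroups. The one nearest to prior diagnosis is "Known cardiac abnormality (with, without"). SAP 2.2 collects prior cardiac diagnoses and cardiac abnormalities as two separate variables.

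**The concern.** Impact is a contrast: US against France, with against without a prior diagnosis, obese against not obese. The planned tables describe each level on its own and leave the contrast to the reader. The point difference can be had by subtraction, but its uncertainty cannot be read off two separate intervals. Two intervals may overlap although the difference excludes zero. One level may clear the 80% goal and the other miss it although the true rates are equal.

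The protocol says the trial is meant to support FDA and CE certification and wider use by non-experts. Whether quality holds up in obese patients and across sites bears on that use. Without a planned contrast, any statement about impact in the report would rest on an informal reading of side-by-side intervals.

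**Working it through.** **Any figure in the plan?** None for this objective. The nearest is the power in SAP 3.5, which concerns the primary endpoints: 0.98^4 = 0.922, so the stated value above 0.92 for four parameters reproduces, and 8 × 30 = 240. Neither figure is affected by this point.

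**Inputs from the documents.** 240 patients, half per centre, so 120 v 120. Eight novices with 30 patients each, so 120/30 = 4 nurses per centre. Two-sided 95% intervals. Performance goal: lower limit above 80%.

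**Assumptions not in the documents.** The success counts and rates, the obese share (20% to 40%) and the nurse ICC (0.01 to 0.05). Exact binomial intervals stand in for the MRMC intervals.

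**1. Overlapping intervals with a difference that excludes zero** (invented counts)
- Centre A: 115/120 = 95.8%, exact 95% CI 90.5 to 98.6.
- Centre B: 105/120 = 87.5%, exact 95% CI 80.2 to 92.8.
- The intervals overlap and both lower limits exceed 80%.
- Difference = 0.9583 − 0.8750 = 0.0833.
- SE = √(0.9583 × 0.0417/120 + 0.8750 × 0.1250/120) = 0.0353.
- 95% CI = 0.0833 ± 1.96 × 0.0353, which is 1.4 to 15.2 points (Fisher p = 0.033).

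**2. The same example with patients clustered by nurse.** Nurses are nested in centre, so the SE is multiplied by √(1 + 29 × ICC).

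| Assumed nurse ICC | Design effect | Half-width (points) | 95% CI (points) |
|---|---|---|---|
| 0 | 1.00 | 6.9 | 1.4 to 15.2 |
| 0.01 | 1.29 | 7.9 | 0.5 to 16.2 |
| 0.02 | 1.58 | 8.7 | -0.4 to 17.0 |
| 0.05 | 2.45 | 10.8 | -2.5 to 19.2 |

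The lower limit reaches zero at an ICC of about 0.016. The example is therefore not evidence of a centre effect. It shows that the answer depends on an uncertainty that the plan does not compute.

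**3. The opposite error.** Suppose both centres have a true rate of 90%. With 120 patients, the exact lower limit exceeds 80% when at least 105 succeed, which has probability 0.856. The chance that exactly one centre clears the limit is 2 × 0.856 × 0.144 = 0.25. For obese v non-obese patients at the same true rate, it is 29% to 53% as the obese share falls from 40% to 20%.

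**4. What the added contrast could deliver.** Half-width = 1.96 × √(p(1 − p)(1/n1 + 1/n2)), independent patients, p = 90%:
- centre, 120 v 120: 7.6 points (9.0 at 85%, 5.5 at 95%);
- obese v not, 48 v 192: 9.5 points; 72 v 168: 8.3; 96 v 144: 7.7;
- centre with an ICC of 0.01 to 0.05: 8.6 to 11.9 points.

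**The case against.** The strongest reply is that the plan does more than list intervals. The repeated analysis includes the novice-minus-expert difference in every subgroup. The expert exam is a same-patient control, so the tables would show whether weaker novice results in obese patients are matched by weaker expert results. A reader might infer that no difference of any kind is estimated; SAP 5.4.1 does not support that. The reply stands, but this difference compares operators within a level. It does not compare levels.

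A reader might also infer that the objective cannot be answered at all, or that impact will be judged by whether intervals overlap. The documents support neither. The objective carries no hypothesis or success criterion, point differences follow by subtraction, and no overlap rule appears anywhere. Misreading of overlap is a risk in use, not a planned method.

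SAP 4.1 does name chi-square and Fisher tests for comparing qualitative variables, and a statistician could apply them here. That convention is assigned to no subgroup comparison, gives a p-value rather than an effect size, and does not allow for nurse or reader. Where the SAP wants a comparison between sites it says so: 5.2 plans one, for demographics and anthropometrics only.

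Finally, centre is confounded with nurse and the intervals will be wide. Both are true. They are reasons to report the uncertainty and its limits, not to leave it out.

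**Conclusion.** The point holds as a gap between an objective and its analysis. For centre, prior cardiac diagnosis and obesity, the SAP plans results within levels but no difference between levels with a CI, either in novice success or in the novice-minus-expert gap. The size and uncertainty of any impact are therefore not estimated. A related mismatch is that the objective names prior cardiac diagnoses while the subgroup is known cardiac abnormality.

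The consequence is moderate. In the illustration an 8.3-point difference sits behind overlapping intervals, but its CI includes zero once the assumed nurse ICC reaches about 0.02. The counts, rates, obese shares and ICCs are assumptions, and binomial intervals replace the MRMC ones. The design effect used for centre does not carry over to obesity or diagnosis, because these can vary within a nurse's own patients. The primary success criterion and the sample size do not depend on this point.

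**What to change.** In SAP 5.4.1 and 5.4.2.1, add for each factor below the between-level difference in novice success and in the novice-minus-expert gap, each with a 95% CI that allows for readers and for clustering by nurse:
- centre: US v France;
- prior cardiac diagnosis: yes v no, using the variable that the objective names and not only known cardiac abnormality;
- obesity: BMI 30 or more v under 30.

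Name the method for the CI, label the results descriptive with no test required, and give the minimum subgroup size below which they will not be reported. State that centre cannot be separated from nurse, with four nurses per site. A contrast by exam sequence number is optional, since it lies outside the stated objective.

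Cost: a little more programming, a choice of method for few clusters, and wide intervals, especially for centre. No new data are needed. Label: cheap improvement.

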5.4.2 Secondary Endpoints Analysis

The analyses will be performed on the FAS population.

5.4.2.1 Quality Endpoints Analysis

For the quality endpoints (enumerated in section 3.4.1), the number and percentage of achievement of qualitative visual assessment according to cardiologist review (at least 3 of 5 cardiologists answer “yes”, that is to say, the majority) and its 95% CI will be evaluated for the novice and the expert. The 95% CI will be computed *via* an MRMC analysis.

For comparison, the difference between the percentage of success for the novices’ exams and the percentage of success for the experts’ exams will be computed, in patients from the FAS population who have exams performed by both novices and experts.

In secondary analyses of quality endpoints, the same analysis will be performed on each subgroup (investigator center, known cardiac abnormality, body mass index, and exam sequence number), depending on the number of patients in each subgroup.

5.4.2.2 Clinical Qualitative Endpoints Analysis

For clinical qualitative endpoints, at least 3 of 5 cardiologists had to answer the endpoint. The value chosen by most cardiologists who answer the endpoint on the experts’ exam will be considered as the reference value. Similarly, the value chosen by most cardiologists who answer the endpoint on the novices’ exam will be considered as the tested value. For both exams, it is possible not to have a majority assessment among cardiologists, as only 4 cardiologists may answer the question.

For each clinical qualitative endpoint, the number of patients for whom both the reference and tested values are the same and are different will be computed. These figures will be presented in a confusion matrix similar to Table 1 (the categories will change according to the endpoint, see categories according to the endpoint in section 3.4.2.1). The percentage of the overall agreement will be calculated for each qualitative endpoint as the corresponding confidence interval.

		Experts' exams				% Overall Agreement and C.I.
		Normal or borderline	Reduced	No majority assessment among cardiologists	Total	
Novices' exams	Normal or borderline					-
	Reduced					-
	No majority assessment among cardiologists					-
	Total					

Table 1: Confusion matrix to compare novices' exams to experts' exams for the endpoint “qualitative visual assessment of right ventricular function”.

It is expected that not many exams will be counted in the “No majority assessment among cardiologists” category, either novice or expert exams. If this is not the case, a sensitive analysis will be conducted.

For each endpoint, the endpoint will be converted into a binary issue, answering the question “Is the structure normal?”, according to the following rules:

- “yes” if the answer to the endpoint is:
 - “normal or borderline” or “structurally normal” or “normal”
 - “absent”
- “no” if the answer to the endpoint is:
 - “hypertrophy”
 - “dilation”
 - “hypertrophy and dilation”
 - “reduced (EF ≤ 50 %)” or “reduced”
 - “present”
 - “abnormal” or “structurally abnormal” or “abnormal (enlarged)”
 - “suspected device”
 - “dilated”

Then, for each endpoint, and on the exams where there is a majority assessment among cardiologists, the following figures will be computed:

- Number of true positives (TP) when both the reference and tested values are positive,
- Number of false positives (FP) when the reference value is negative and the tested value is positive,
- Number of false negatives (FN) when the reference value is positive and the tested value is negative,
- Number of true negatives (TN) when both the reference and tested values are negative.

In addition, based on these figures, the following metrics will be computed:

- Accuracy, calculated using the formula: $(TP + TN) / (TP + FP + FN + TN)$,
- Sensitivity (= recall), calculated using the formula: $TP / (TP + FN)$,
- Specificity, calculated using the formula: $TN / (TN + FP)$,
- Precision, calculated using the formula: $TP / (TP + FP)$,
- F1-score, calculated using the formula: $2 \times (\text{precision} \times \text{recall}) / (\text{precision} + \text{recall})$.

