2.2 Collected Data

The following data will be collected for both the exam acquired by the expert and the exam acquired by the novice:

- Whether the exam was acquired by the expert/novice,
- Reason for not acquiring the exam,
- Whether the exam has successfully been exported for review by the cardiologists,
- Number of clips acquired by the expert/novice,
- Novice acquisition duration in minutes,
- Report of Adverse event (AE) with details, start and end date, severity, relationship, action taken and outcome,
- Report of Device deficiency (DD) with details, date, type, and reason of deficiency, action taken and outcome,
- Report of Serious adverse event (SAE) with details, start and end date, severity, relationship, action taken, and outcome.

The following data will be collected for each review performed by each cardiologist on each exam for qualitative assessment:

- Qualitative assessments
- For the 10 reference views of cardiac ultrasound (PLAX, PSAX-PM, PSAX-MV, PSAX-AV, A4C, A5C, A2C, A3C, SC-4C and SC-IVC), quality of diagnostic (Yes/No/No clip),
- Qualitative visual assessment of left ventricular size (Yes/No) and type* (if Yes),
- Qualitative visual assessment of left ventricular function (Yes/No) and type* (if Yes),
- Qualitative visual assessment of right ventricular size (Yes/No) and type* (if Yes),
- Qualitative visual assessment of right ventricular function (Yes/No) and type* (if Yes),
- Qualitative visual assessment of non-trivial pericardial effusion (Yes/No) and type* (if Yes),
- Qualitative visual assessment of left atrial size (Yes/No) and type* (if Yes),
- Qualitative visual assessment of right atrial size (Yes/No) and type* (if Yes),
- Qualitative visual assessment of segmental kinetics of the left ventricle (Yes/No) and type* (if Yes),
- Qualitative visual assessment of aortic valve (Yes/No) and type* (if Yes),
- Qualitative visual assessment of mitral valve (Yes/No) and type* (if Yes),
- Qualitative visual assessment of tricuspid valve (Yes/No) and type* (if Yes),
- Qualitative visual assessment of inferior vena cava size (Yes/No) and type* (if Yes).

* For each assessment, the type will be described in section 3.4.1.

The following data will be collected for each review performed by each cardiologist on each exam for quantitative assessment:

- For PLAX clip:
 - If measurement = Yes, IVSd, LVEDD, and PWd measurement (in mm),
 - If measurement = Yes, LVESD measurement (in mm),

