3.4.2 Clinical Endpoints

3.4.2.1 Qualitative Endpoints

Indicate the evaluation when the entire exam allows the qualitative visual assessment of

- left ventricular size (normal or borderline, hypertrophy, dilation, hypertrophy and dilation),
- global left ventricular function (normal or borderline, reduced (EF ≤ 50 %)),
- right ventricular size (normal or borderline, hypertrophy, dilation, hypertrophy and dilation),
- non-trivial pericardial effusion (absent, present),
- right ventricular function (normal or borderline, reduced),
- left atrial size (normal or borderline, abnormal (enlarged)),
- right atrial size (normal or borderline, abnormal (enlarged)),
- segmental kinetics of the left ventricle (normal or borderline, abnormal),
- mitral valve (structurally normal, structurally abnormal, suspected device),
- tricuspid valve (structurally normal, structurally abnormal, suspected device),
- aortic valve (structurally normal, structurally abnormal, suspected device),
- inferior vena cava size (normal, dilated),

Any other abnormalities (free text) that can be visually assessed will be described in listings.

NB: For visual assessment of left ventricular size and right ventricular size, the choices "hypertrophy," "dilation," and "hypertrophy and dilation" can be grouped in a more general category: "abnormal (enlarged)."

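### Sensitivity and specificity in SAP 5.4.2.2 cover only pairs in which both exams were readable, so they do not give the share of expert-found abnormalities that novice exams show

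*SAP*

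**What the plan says.** - **What readers record.** Under SAP 2.2 each reader first states whether a structure can be assessed and gives a type only after a yes. SAP 3.4.2.1 frames the clinical qualitative endpoints the same way: "Indicate the evaluation when the entire exam allows the qualitative visual assessment of" the listed structures.
- **How a value is formed.** SAP 5.4.2.2 states that "at least 3 of 5 cardiologists had to answer the endpoint". Then "The value chosen by most cardiologists who answer the endpoint on the experts’ exam will be considered as the reference value", and "the value chosen by most cardiologists who answer the endpoint on the novices’ exam will be considered as the tested value".
- **What is counted.** Answers are reduced to whether the structure is normal, and the cells TP, FP, FN and TN are filled "on the exams where there is a majority assessment among cardiologists". A false negative needs a positive reference value and a negative tested value. Accuracy, sensitivity, specificity, precision and F1 are built from these four cells.
- **Table 1.** The confusion matrix has a row and a column for no majority, which the text explains by the chance that only four readers answer. It has none for fewer than three answers. Overall agreement is presented with this table. A further analysis is promised if the no-majority category is not small, without a threshold or method.
- **Missing data.** SAP 4.3 replaces nothing and reports the number missing.
- **Aim.** One secondary objective in SAP 3.2 is "to evaluate the agreement between the acquisitions obtained by experts and those obtained by novices". The protocol's Analysis section also takes the expert acquisition as the reference.

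**The concern.** Whether a patient enters the 2x2 counts depends partly on whether the novice exam could be read, and novice image quality is what the trial tests. Suppose the expert exam shows an abnormality and the novice exam is too poor for three readers to answer. The patient then leaves the calculation and is not recorded as an abnormality the novice exam failed to show.

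An unqualified sensitivity is easily taken to mean the share of abnormalities that novice exams reveal. The planned figure answers a narrower question: how often the two exams agree when both are readable. The protocol says the trial is meant to support FDA and CE certification, so the reported number should carry the right meaning.

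**Working it through.** The documents give no expected sensitivity, specificity, agreement, prevalence or non-assessable rate for these endpoints, so there is no stated figure to reproduce. The check is a trace of the rules, followed by illustrations on assumed inputs.

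**1. Trace of one patient.** The expert exam is read as abnormal by the majority, so a reference value exists. The novice exam gets 0, 1 or 2 answers because the other readers say the structure cannot be assessed (SAP 2.2, 3.4.2.1). The three-answer minimum is not met, so there is no tested value. TP and FN each need a tested value, so the patient is in neither and drops out of TP + FN. A novice exam with a tie drops out in the same way, because the counts are limited to exams with a majority. If the sponsor meant the no-majority category to include fewer than three answers, these exams would appear in Table 1 but still not in TP, FP, FN or TN.

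**2. What the planned tables offer instead.** SAP 5.4.1 and 5.4.2.1 report the percentage of assessable exams for novices and experts, overall and by subgroup, including known cardiac abnormality (SAP 4.2.5). That subgroup is defined per patient, not by the expert finding for each structure. No planned table gives the non-assessable share among patients whose expert exam is abnormal for that structure.

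**3. Formula.** Let s be sensitivity for abnormality among pairs with both values, and u the share of reference-abnormal patients whose novice exam has no tested value. With D reference-abnormal patients, the share shown as abnormal is D(1 − u)s / D = s(1 − u). The planned figure stays at s whatever u is.

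With s = 0.90 (assumed) and u assumed:
- u = 5%: 0.90 × 0.95 = 0.855
- u = 10%: 0.90 × 0.90 = 0.81
- u = 20%: 0.90 × 0.80 = 0.72

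**4. How many novice exams could be lost.** For the four primary structures, an exam that fails the three-of-five rule in SAP 5.4.1 is also one with fewer than three answers here. The exact 95% interval is used as a stand-in for the planned MRMC interval. On that basis 205/240 (85.4%) has a lower limit of 80.3% and meets the 80% goal, and 204/240 has 79.8% and does not. A primary endpoint could therefore succeed with 35/240 = 14.6% of novice exams not assessable. The quality endpoints in SAP 3.4.1 have no such goal.

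**5. Why overall assessability cannot fill the gap.** Assume 240 patients with both exams, a reference value for all, 20% abnormal (48 abnormal, 192 normal), no ties, and about 90% sensitivity and 95% specificity among readable pairs.

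| Quantity | Scenario A | Scenario B |
|---|---|---|
| Not assessable: abnormal / normal | 7 / 28 | 10 / 10 |
| Not assessable overall | 35/240 = 14.6% | 20/240 = 8.3% |
| TP, FN, TN, FP | 37, 4, 156, 8 | 34, 4, 173, 9 |
| Planned sensitivity | 37/41 = 90.2% | 34/38 = 89.5% |
| Read as abnormal, all reference-abnormal | 37/48 = 77.1% | 34/48 = 70.8% |
| Planned specificity | 156/164 = 95.1% | 173/182 = 95.1% |
| Read as normal, all reference-normal | 156/192 = 81.3% | 173/192 = 90.1% |
| Planned accuracy | 193/205 = 94.1% | 207/220 = 94.1% |
| Agreement over all 240 | 193/240 = 80.4% | 207/240 = 86.3% |

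Scenario B loses fewer exams overall yet shows fewer of the abnormalities, and the planned figures hardly differ between the two.

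**The case against.** **The conditional measure is declared.** SAP 3.4.2.1 defines these endpoints as the evaluation given when the exam permits one. Agreement among readable exams is a legitimate question, and a reader who answers not assessable has not called the structure normal. This stands. A reader might infer that the planned figures are wrong or biased. They are not wrong for the question they answer, and counting an unreadable exam as not showing the abnormality is a second measure to set beside them.

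**Failures are counted elsewhere.** Non-assessability is the subject of the primary and quality endpoints, including a breakdown by known cardiac abnormality. It is therefore not hidden. The objection stands to that extent, but those rates are not tied to the expert finding for each structure.

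**A further analysis is already promised.** SAP 5.4.2.2 plans one if many exams have no majority. As the text explains that category, it concerns ties and not too few answers, and the analysis has no trigger or method. It helps only in part.

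**Overall agreement.** A reader might infer that agreement also drops these exams. The documents do not show this. The majority restriction is attached to TP, FP, FN and TN and the metrics built on them. Table 1 displays no-majority exams and totals, and the agreement denominator is not stated.

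**The positive class is undefined.** The SAP's binary question asks whether the structure is normal, with yes for normal, and never says which answer is positive. If normal is positive, detection of abnormality is the specificity and the same loss falls there. The calculations above take abnormal as positive.

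**The size is illustrative.** For the primary structures, a 20% loss among abnormal patients would need them to be over-represented among the unreadable exams, or a failed primary endpoint. Patients with previously reported poor echogenicity are also excluded. Both points are fair.

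**Conclusion.** The point holds for the TP/FP/FN/TN counts and the metrics derived from them. An expert-found abnormality paired with a novice exam that has fewer than three answers, or no majority, is not counted as missed, and no planned output lets the reader recover how many such patients there are. The planned figures remain valid as performance conditional on both exams being readable.

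The size is s(1 − u), and both terms are assumptions. At s = 90%, shares of 5%, 10% and 20% give 85.5%, 81% and 72%. If few reference-abnormal patients have unreadable novice exams, the two sets of figures will nearly coincide.

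For overall agreement the finding is an unstated denominator and no more. These endpoints are secondary and SAP 3.3 sets a success criterion only for the primary ones, so the primary conclusion is unaffected. Pairs whose expert exam has no reference value cannot be counted as missed and stay outside both sets of figures.

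**What to change.** 1. Keep the planned figures and label them as conditional on both exams being assessable.
2. Add a row and a column to Table 1 for not assessable (fewer than three answers), state the denominator of overall agreement, and define abnormal as the positive class.
3. Beside the planned figures, report over all patients with both exams and an expert reference value: (a) the proportion of reference-abnormal patients whose novice exam was read as abnormal; (b) the proportion of reference-normal patients whose novice exam was read as normal; (c) overall agreement. In each, a non-assessable or no-majority novice exam stays in the denominator and counts as not agreeing.
4. Show the number of such novice exams by reference status.
5. Leave precision and F1 conditional. Entering an unreadable exam as a false positive would invent a reading nobody made.

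The cost is one more set of figures per table, from data already collected. That set will be lower wherever any such novice exam occurs. This is a cheap improvement.
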